5.2 Cytarabine

Mechanism of action: Cytarabine works by inhibition of DNA synthesis. Cytosine gains entry into cells by a carrier process, and then must be converted to its active compound, aracytidine triphosphate. Cytosine is a pyrimidine analog, which is incorporated into DNA; however, its primary action is inhibition of DNA polymerase resulting in decreased DNA synthesis and repair.

Product description: Cytarabine (conventional) is commercially available in vials containing 20 mg/ml (25 ml) and 100 mg/ml (20 ml) solution for injection and are stable at room temperature.

Solution preparation: Cytarabine can be compounded in 100-1000 ml of NS or D5W and is stable at room temperature for 48 hours once compounded. Cytarabine solutions reconstituted with diluents containing benzyl alcohol should not be used for intrathecal injections or for IV administration of high dose cytarabine (> 1

gm/m²). Solutions for parenteral administration are generally reconstituted to concentrations ranging from 20-100 mg/ml, depending on the dose and the route of administration.

Solutions are stable at room temperature for 7 days, but use within 48 hours of preparation, or refrigerated for 24 hours beyond use date, is recommended by the manufacturer. Furthermore, solutions prepared with diluents which do not contain preservative or bacteriostat, should be used within 8 hrs of vial entry to minimize the risk of bacterial contamination.

Premedication: Dexamethasone 0.1% ophthalmic eye drops should be administered >1 hour prior to cytarabine infusion to both eyes and continued Q6hours through day 12 of treatment.

Route of administration: Cytarabine will be administered intravenously in a dose that adjusted due to age: <60 years: 2 gm/m² IV Q12hours days 1-5; ≥60 years: 1.5 gm/m² IV Q12hours days 1-5 over 2 hours. The infusion should not be interrupted for the delivery of blood products, antibiotics, etc.

Handling and Disposal: Please see policy on hazardous drugs:
<http://intranet.unchealthcare.org/intranet/hospitaldepartments/safetynet/policies/hazardousdrugs.pdf/view>

5.3 Adverse Events Associated with Cytarabine

Serious and Common Adverse Effects:

The most common toxicities associated with cytarabine, even when used at doses ≤200mg/m² include hematologic (neutropenia, thrombocytopenia, anemia), gastrointestinal (nausea & vomiting (this agent is highly emetogenic), diarrhea and mucositis), dermatologic (rash), hepatic (hepatic dysfunction, mild jaundice, transaminase elevations), non-infectious fever, and alopecia. Additional toxicities associated with high dose cytarabine (≥ 1gm/m²) include neurologic (primarily cerebellar such as nystagmus, ataxia, abnormal gait), but also cerebral such as somnolence, psychosis, confusion seizures), ocular toxicity, and rarely pulmonary edema.

6.0 EVALUATIONS AND ASSESSMENTS

6.1 Time and Events Table

Assessment	Treatment Schedule for Cycle 1 (INDUCTION)									Full Heme Recovery or on D45 +/- 2 days ²	For patients in ≥PR post recovery ³ D1 each cycle; continue cycles for 2 years of MAINTENANCE	EOT ⁴	Follow-up ⁵
	Pre-study ¹	D1 Cycle 1	D2 Cycle 1	D3 Cycle 1	D4 Cycle 1	D5 Cycle 1	D 6-13 Cycle 1	D14 Cycle 1	Daily from D15 until early heme recovery or discharge from hospital ¹³				
Informed Consent	X												
History ⁶	X	X	X	X	X	X		X			X ⁶	X ⁶	X
Physical exam ⁶	X	X						X		X	X	X	X
Performance Status	X	X									X	X	
Pregnancy Test ⁷	X							X					
Echocardiogram	X												
CBC with differential	X	X	X	X	X	X	X	X	X	X	X	X	X
Serum chemistries ⁸	X	BID	BID	BID	BID	BID	X	X	X	X	X	X	X
LDH, Uric acid, phosphate ⁸	X	BID	BID	BID	BID	BID	X ⁸	X					
Liver function tests ⁹	X	X	X	X	X	X	X ⁹	X	X ⁹	X ⁹	X	X	X
Coagulation labs ⁹	X	X	X	X	X	X		X					
Thyroid function tests ¹⁰	X							X			X		
Concomitant meds	X	X	X	X	X	X	X	X	X		X	X	X
Toxicity Assessment		X	X	X	X	X	X	X	X	X	X	X ⁴	X ³
Bone marrow	X ¹¹										X ¹¹	X ¹¹	
Blood sample for biomarkers and buccal cell collection	X ¹²							X ¹²	Weekly ¹²		X ¹²	X ¹²	
Cytarabine IV every 12 hours		X	X	X	X	X							

LCCC 1522
PI: [name]
June 02, 2018

CONFIDENTIAL
UNIVERSITY OF NORTH CAROLINA

Amendment 07

Pembrolizumab 200mg IV								X				X		
Survival analysis														X
QOL Questionnaire ¹⁴												X		

Key to Time and Events Table Footnotes

¹ Unless otherwise noted, evaluations may be performed up to 2 weeks prior to Cycle 1 Day 1 of treatment. Cycle 1 Day 1 laboratory assessments do not need to be repeated if they have been performed up to 72 hours prior to the scheduled visit. **NOTE:** A window of 2 days will be applied to all study visits.

² Full hematologic recovery is defined as absolute neutrophil count $\geq 1,000/\text{mcL}$ and platelet count $\geq 100,000/\text{mcL}$. All assessments listed including a disease assessment via bone marrow biopsy will occur at hematologic recovery, or by day 45 +/- 2 days, whichever comes first. See section 4.2 for additional details regarding D14 pembrolizumab delay.

³ Patients in $\geq \text{PR}$ based on BM biopsy may continue to receive pembrolizumab every 21 days +/- 3 days (1 cycle) until maintenance treatment duration totals 1 year (see section 4.3 for additional details), disease progression, or intolerable toxicity, whichever occurs first. Pembrolizumab will start 10-60 days post full hematologic recovery in those who achieve PR or CR, and 10-60 days post the post induction bone marrow biopsy in those who achieve CRi. Patients who do not achieve at least a PR, or receive pembrolizumab maintenance by day 60 of hematologic recovery (or day 60 post-induction bone marrow biopsy in CRi patients) will be taken off of protocol-mandated therapy and followed up per protocol.

⁴ This end of treatment (EOT) visit should occur in patients when they stop treatment whether due to disease progression, unmanageable toxicity, or they have reached 2 years of treatment, and will take place ~30 days post last dose of pembrolizumab. Patients who experience $\geq \text{Grade 2}$ treatment-related adverse event will be contacted every 2 weeks until the event is resolved to Grade 0 or 1, determined to be irreversible by the investigator, or until the patient begins an alternate form of drug treatment.

⁵ The first long-term follow-up visits will take place ~60 days after the EOT visit (+/- 15 days) and will focus on any serious adverse events (SAEs) or any grade of Events of Clinical Interest (see section 7.3.4.1) that occur within 90 days of the end of pembrolizumab (or prior to start of new anti-cancer therapy). Any such events must be recorded. Subsequent long-term follow up visits will take place at a schedule as per institutional standard of care (i.e., usually every ~3-6 months) and will be limited to history of any subsequent cancer treatments, an assessment of any SAE's considered to be possibly or probably related to study treatment until resolution, and survival status.

⁶ Complete history at baseline only, thereafter focused history on symptoms/toxicity. Physical exam to include height (baseline only), weight (D1 and D14 of cycle 1, D1 of all cycles of maintenance pembrolizumab and all follow-up visits) and vital signs

⁷ Serum or urine B-HCG within 72 hours prior to D1 of HiDAC and prior to D14 pembrolizumab, and only if clinically appropriate; if the urine test is positive or cannot be confirmed as negative, a serum pregnancy test will be required.

⁸ Serum chemistries include Na, K, Cl, creatinine, BUN, calcium, magnesium, bicarbonate, and glucose; serum chemistries along with LDH, uric acid, and phosphate comprise tumor lysis labs. During induction, tumor lysis labs should be assessed BID (twice daily) D1-5, and once daily from D6 until tumor lysis syndrome is resolved, which usually occurs by D10. Repeat LDH, uric acid and phosphate on D14.

⁹ Liver function tests (LFTs) include total protein, albumin, total bilirubin, alkaline phosphatase, ALT, and AST (**NOTE:** on D6-13, and on D15 through recovery, LFTs only required every other day); coagulation labs include PT/INR, aPTT, D-Dimer and fibrinogen

¹⁰Thyroid tests include T3, free T4, TSH as denoted during induction therapy. These tests should be performed on D1/C1 prior to starting maintenance therapy with pembrolizumab and repeated every 3 cycles thereafter (i.e., cycles 3, 6, 9, 12, etc.) until treatment discontinuation.

¹¹Initial (pre-treatment) bone marrow biopsy should be obtained within 14 days prior to D1 of HiDAC as per standard of care. Patients will undergo repeat bone marrow at time of full hematologic recovery or on D45 +/- 2 days whichever comes first as per standard of care. Repeat biopsy after every 4 cycles of maintenance during year 1 and every 6 cycles of maintenance during year 1-2. Each time a bone marrow biopsy is done as per standard of care, additional 4x8mL will be collected in green top ACD tubes (~32 mL) for correlative studies. See section 6.7 and the laboratory manual for additional details. Repeat biopsy at any time if there is a suspicion of leukemia recurrence either during maintenance phase or in follow-up.

¹²Buccal cell collection should be collected from all patients during screening. If not done during screening, this can be performed at any point during follow-up. Please see laboratory manual for details. For peripheral blood samples for research, collect 5 x8mL ACD green top tubes of blood (~40mLs) pre-treatment within 14 days prior to D1 of HiDAC, D14 (1-12 hours prior to pembrolizumab administration), weekly between D14 and hematologic recovery (i.e. D21, D28, D35, and D42 (the latter if no full hematologic recovery by this time) and at full hematologic recovery or on D45+/- 2 days whichever occurs first. Repeat blood sample on D1 of each maintenance cycle of pembrolizumab during year 1 and every even cycle of maintenance during year 1-2. Repeat blood sample at any time if there is a suspicion of leukemia recurrence either during maintenance phase or in follow-up. See section 6.7 and the laboratory manual for additional details.

¹³Patients discharged from the hospital prior to early recovery should receive CBC, serum chemistries, and liver function tests at minimum three times weekly until early recovery

¹⁴Should be completed during each cycle of maintenance therapy (ie, day 1 of each cycle). Completion of the questionnaire will be optional.

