4.3.1 Toxicities and Dose Modifications for Pembrolizumab Maintenance

Adverse events (both non-serious and serious) associated with pembrolizumab exposure may represent an immunologic etiology. These adverse events may occur shortly after the first dose or several months after the last dose of treatment. Pembrolizumab must be withheld for drug-related toxicities and severe or life-threatening AEs as per Table 3 below. See section 4.4 for supportive care guidelines, including use of corticosteroids.

Dosing interruptions are permitted in the case of medical / surgical events or logistical reasons not related to study therapy (e.g., elective surgery, unrelated medical events, patient vacation, and/or holidays). Subjects should be placed back on study therapy within 3 weeks of the scheduled interruption, unless otherwise discussed with the Sponsor. The reason for interruption should be documented in the patient's study record.

If a dose of pembrolizumab is delayed, then the subsequent dose should be administered 3 weeks later. Patients may receive up to 1 year of treatment with pembrolizumab beginning on day 1 of maintenance therapy. In the event of dose delays/interruptions, subjects may not receive more than 1 total year of treatment beginning with day 1 of maintenance therapy.

Table 3. Dose Modifications

General instructions:				

 1. Corticosteroid taper should be initiated upon AE improving to Grade 1 or less and continue to taper over at least 4 weeks. 2. For situations where pembrolizumab has been withheld, pembrolizumab can be resumed after AE has been reduced to Grade 1 or 0 and corticosteroid has been tapered. Pembrolizumab should be permanently discontinued if AE does not resolve within 12 weeks of last dose or corticosteroids cannot be reduced to ≤ 10 mg prednisone or equivalent per day within 12 weeks. 3. For severe and life-threatening irAEs, IV corticosteroid should be initiated first followed by oral steroid. Other immunosuppressive treatment should be initiated if irAEs cannot be controlled by corticosteroids. 				
Immune-related AEs	Toxicity grade or conditions	Action taken to pembrolizumab	irAE management with corticosteroid and/or other therapies	Monitor and follow-up

Amendment 07

	(CTCAEv4.0)			

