Nephritis occurred in 3 (0.7%) patients of melanoma patients treated in clinical trials of pembrolizumab, consisting of one case of Grade 2 autoimmune nephritis (0.2%) and two cases of interstitial nephritis with renal failure (0.5%), one Grade 3 and one Grade 4. The time to onset of autoimmune nephritis was 11.6 months after the first dose of pembrolizumab (5 months after the last dose) and lasted 3.2 months; this patient did not have a biopsy. Acute interstitial nephritis was confirmed by renal biopsy in two patients with Grades 3-4 renal failure. All three patients fully recovered renal function with treatment with high-dose corticosteroids (greater than or equal to 40 mg prednisone or equivalent per day) followed by a corticosteroid taper.

Immune-Mediated Hyperthyroidism

Hyperthyroidism occurred in 5 (1.2%) of 411 melanoma patients treated in clinical trials of pembrolizumab. The median time to onset was 1.5 months and the median duration was 2.8 months (range 0.9 to 6.1). One of two patients with Grade 2 and the one patient with Grade 3 hyperthyroidism required initial treatment with high-dose corticosteroids (greater than or equal to 40 mg prednisone or equivalent per day) followed by a corticosteroid taper. One patient (0.2%) required permanent discontinuation of pembrolizumab due to hyperthyroidism. All five patients with hyperthyroidism experienced complete resolution of the event.

Immune-Mediated Hypothyroidism

Hypothyroidism occurred in 34 (8.3%) of 411 melanoma patients treated in clinical trials of pembrolizumab. The median time to onset of hypothyroidism was 3.5 months. All but two of the patients with hypothyroidism were treated with long-term thyroid hormone replacement therapy. The other two patients only required short-term thyroid hormone replacement therapy. No patient received corticosteroids or discontinued pembrolizumab for management of hypothyroidism. Thyroid disorders can occur at any time during treatment.

Other Immune-Mediated Adverse Reactions

Other clinically important immune-mediated adverse reactions can occur. The following clinically significant, immune-mediated adverse reactions occurred in less than 1% of patients treated with pembrolizumab, including exfoliative dermatitis, uveitis, arthritis, myositis, pancreatitis, hemolytic anemia, partial seizures arising in a patient with inflammatory foci in brain parenchyma, and adrenal insufficiency.

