6.8 Assessment of Safety

Any patient who receives pembrolizumab treatment on this protocol will be evaluable for toxicity. Each patient will be assessed periodically for the development of any toxicity according to the Time and Events table (6.0). Toxicity will be assessed according to NCI CTCAE v4. Toxicities will be characterized in terms of seriousness, causality, toxicity grading, and action taken with regard to trial treatment.

For subjects receiving treatment with pembrolizumab, all AEs of unknown etiology associated with pembrolizumab exposure should be evaluated to determine if it is possibly an event of clinical interest (ECI) of a potentially immunologic etiology (termed immune-related adverse events, or irAEs); see the separate ECI guidance document (provided as a document separate from this protocol) regarding the identification, evaluation and management of potential irAEs.

Please refer to section 7.0 for detailed information regarding the assessment and recording of AEs.

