7.2 Documentation of non-serious AEs or SARs

For non-serious AEs or SARs, documentation must begin from day 1 of study treatment and continue through the 30 day follow-up period after treatment is discontinued.

Collected information should be recorded in the Case Report Forms (CRF) for that patient. Please include a description of the event, its severity or toxicity grade, onset and resolved dates (if applicable), and the relationship to the study drug. Documentation should occur at least monthly.

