7.3.4.1 Events of Clinical Interest

Selected non-serious and serious adverse events are also known as Events of Clinical Interest (ECI) and must be reported within 24 hours to the LCCC Multicenter Project Manager who will report the event within 2 working days to Merck Global Safety. (Attn: Worldwide Product Safety; [contact])

For the time period beginning when the consent form is signed until treatment allocation/randomization, any ECI, or follow up to an ECI, that occurs to any

subject must be reported within 24 hours to the Sponsor and within 2 working days to Merck Global Safety if it causes the subject to be excluded from the trial, or is the result of a protocol-specified intervention, including but not limited to washout or discontinuation of usual therapy, diet, placebo treatment or a procedure.

For the time period beginning at treatment allocation/randomization through 90 days following cessation of treatment, or 30 days following cessation of treatment if the subject initiates new anticancer therapy, whichever is earlier, any ECI, or follow up to an ECI, whether or not related to Merck product, must be reported within 24 hours to the Sponsor and within 24 hours to Merck Global Safety.

Events of clinical interest for this trial include:

1. an overdose of Merck product, as defined in Section 5.1.10 - Definition of an Overdose for This Protocol and Reporting of Overdose to the Sponsor, that is not associated with clinical symptoms or abnormal laboratory results.
2. an elevated AST or ALT lab value that is greater than or equal to 3X the upper limit of normal and an elevated total bilirubin lab value that is greater than or equal to 2X the upper limit of normal and, at the same time, an alkaline phosphatase lab value that is less than 2X the upper limit of normal, as determined by way of protocol-specified laboratory testing or unscheduled laboratory testing.*

*Note: These criteria are based upon available regulatory guidance documents. The purpose of the criteria is to specify a threshold of abnormal hepatic tests that may require an additional evaluation for an underlying etiology.

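### Event of Clinical Interest has two meanings in the protocol, so non-serious immune-related events that start after the 30-day window and within 90 days of pembrolizumab may go unrecorded or be recorded unevenly across sites

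*Combined protocol and SAP*

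**What the plan says.** **Recording windows.** Section 7.2 has non-serious events documented from day 1 and says this must "continue through the 30 day follow-up period after treatment is discontinued". Section 7.3.1 takes serious events to 90 days, or to the start of new anti-cancer treatment if earlier. Footnote 5 in section 6.1 adds, for the same 90 days and with the same cut-off, "any grade of Events of Clinical Interest (see section 7.3.4.1) that occur within 90 days of the end of pembrolizumab". Section 6.6 repeats that rule without the pointer to 7.3.4.1.

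**Meaning of the term.** Section 6.8 asks whether an unexplained event after pembrolizumab is "possibly an event of clinical interest (ECI) of a potentially immunologic etiology (termed immune-related adverse events, or irAEs", and for identification, evaluation and management tells the reader to "see the separate ECI guidance document (provided as a document separate from this protocol". Section 4.5.2 also uses the term in the immune sense, as the exception to the ban on systemic corticosteroids. Section 7.3.4.1 opens its list with "Events of clinical interest for this trial include" and gives two items: overdose without symptoms or abnormal laboratory results, and AST or ALT at least 3 times ULN with bilirubin at least 2 times ULN and alkaline phosphatase below 2 times ULN. Section 4.5.1 cites 7.2 for the definition, but 7.2 has none.

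**Late onset.** Section 4.3.1 says of immune-type events: "These adverse events may occur shortly after the first dose or several months after the last dose of treatment".

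**The concern.** The secondary objectives include characterising the toxicity of induction (2.2.3) and of pembrolizumab maintenance (2.2.4). The protocol itself expects delayed immune toxicity. A site that works from the schedule and follows footnote 5 arrives at a list with no pneumonitis, colitis, thyroid, pituitary, renal, skin or cardiac event on it. A site that works from 6.8 treats all of these as Events of Clinical Interest. The two sites could collect different data after the 30-day window closes. Wherever the narrow list is used, the reported rate of non-serious immune toxicity would be too low.

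The unacceptable-toxicity rate in 2.4.2 could also be touched. It counts drug-related grade 3 non-hematologic events lasting more than 7 days, with named exceptions, whether or not they are serious.

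**Working it through.** The plan states no figure to reproduce. The check sets the sections side by side and adds some day arithmetic.

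**1. One event, two readings.** Take a non-serious, drug-related grade 2 colitis that starts after the 7.2 window has closed and before day 90 after pembrolizumab, with no new anti-cancer therapy.

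| Sections followed | Event of Clinical Interest? | Must it be recorded? |
|---|---|---|
| Footnote 5 with the 7.3.4.1 list taken as complete | No | No |
| 6.6 with the meaning in 6.8 and 4.5.2 | Yes, any grade | Yes, to 90 days |

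Immune hepatitis is captured on both readings only if it meets the full liver-test pattern. An isolated transaminase rise without the bilirubin criterion does not.

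**2. Which meaning was intended?** Footnote 5 asks for events of any grade. That qualifier suits neither listed item: a symptom-free overdose has no toxicity grade, and the liver pattern has fixed thresholds. It does suit immune-related events, which suggests that the broader meaning was intended.

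**3. Length of the exposed interval.** This depends on when treatment counts as discontinued, which 7.2 does not define.
- Dated at the last pembrolizumab dose: the window closes at day 30 after that dose. The exposed interval is days 31-90, that is 90 - 30 = 60 days.
- Dated at the response assessment (4.6 lists failure to respond as a stopping reason; 4.2 sets the assessment at recovery or day 45 +/- 2): for a non-responder assessed on day 45, the window closes at study day 45 + 30 = 75. After a day-14 dose that is 75 - 14 = 61 days. The exposed interval is days 62-90, that is 90 - 61 = 29 days. An earlier assessment would close the window sooner.

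New anti-cancer therapy shortens either interval.

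**4. The existing visit.** End of treatment is about 30 days after the last dose (footnote 4). First follow-up is about 60 +/- 15 days later (footnote 5). So 30 + 60 +/- 15 gives about days 75-105 after the last dose.

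**5. Onset times in 5.1.6, at 30.4 days per month.**
- Hepatitis (Grade 4): 22 days.
- Hypophysitis: 1.3 months, about 40 days (Grade 2), and 1.7 months, about 52 days (Grade 4).
- Hyperthyroidism: median 1.5 months, about 46 days.
- Hypothyroidism, pneumonitis and colitis: medians 3.5, 5 and 6.5 months, all beyond 90 days.
- Autoimmune nephritis: "11.6 months after the first dose of pembrolizumab (5 months after the last dose", also beyond 90 days.

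The 40-, 46- and 52-day figures fall in days 31-90 on the first dating above, but inside the 7.2 window on the second. The Grade 4 hypophysitis would ordinarily be serious under 7.1.4, and so recorded to 90 days anyway. These times come from melanoma patients and can only indicate what might happen after a single dose.

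**6. Share of non-responders, who receive a single dose.** Share = 1 - CR/CRi rate - PR rate. Section 8.1 takes the PR rate as 0 to 0.05 under the null. Using the same range at the alternative is an assumption.
- Null: 1 - 0.20 - (0 to 0.05) = 0.75 to 0.80.
- Alternative: 1 - 0.40 - (0 to 0.05) = 0.55 to 0.60.

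**7. Related loose ends.** Section 7.3.4.1 gives 2 working days for reporting to the manufacturer in its opening paragraph, and 24 hours in the paragraph on the period after treatment allocation. Through the empty pointer in 4.5.1, the rule for concomitant drugs after 30 days, including steroids given for an immune event, rests on an undefined term.

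**The case against.** A reader might infer that late non-serious immune toxicity definitely goes unrecorded. The documents do not support that, for four reasons.

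- The list in 7.3.4.1 uses the verb *include*, so it need not be complete, and 6.8 relies on a separate guidance document that is not available here.
- Section 6.6 carries no pointer to the short list. Read with 6.8, it requires recording.
- Footnote 5 says the visit focuses on serious events and Events of Clinical Interest, which does not exclude others. The Follow-up column also marks history, physical examination, laboratory tests and a Toxicity Assessment, and 6.8 calls for assessment of any toxicity according to that table.
- The 30 days in 7.2 have no defined start, so the gap may be roughly half as long as it first appears.

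All four stand, and they limit the point to ambiguity and possible loss. They do not remove it. The guidance document is described as covering identification, evaluation and management, not the recording window, and footnote 5 does not cite it. The Toxicity Assessment mark carries superscript 3, which leads to the footnote on maintenance dosing and sets no scope for follow-up. Assessing a patient is not the same as a duty to record: after the 7.2 window, the only explicit recording duty for new events covers serious events and Events of Clinical Interest. The two-weekly contacts in footnote 4 follow existing events and do not look for new ones.

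It is also fair to say that the effect is limited. No immune-event rate appears among the visible endpoints, and most drug-related events of grade 4 or higher would be serious and so captured to 90 days. The likely loss is in lower-grade descriptive tables, with a smaller possible effect on non-serious persistent grade 3 events.

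**Conclusion.** The inconsistency is real and the sections must be reconciled. Non-serious immune-related events that start after the 7.2 window and within 90 days of pembrolizumab may go unrecorded, or be recorded at some sites and not others. Any resulting bias in descriptive immune-toxicity rates would be downward. A possible effect on the 2.4.2 rate cannot be excluded.

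The size of the loss cannot be estimated from the documents. The exposed interval is 60 days if discontinuation is dated at the last dose, and about 29 days for a non-responder if it is dated at a day-45 assessment; new anti-cancer therapy shortens both. Non-responders are about 75-80% of patients at the null and 55-60% at 40% CR/CRi, assuming 0-5% PR. A reader might take the onset times in 5.1.6 as a measure of how many events would be missed. They do not support that: they are few, come from another disease, and include Grade 4 events that would ordinarily be reported as serious.

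The conclusion assumes that at least some sites follow footnote 5 and take the two-item list as complete.

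**What to change.** - In 7.3.4.1, list adverse events of suspected immunologic etiology, of any grade, as events to be recorded. Keep them separate from the two existing items that need expedited reporting.
- Make footnote 5, 6.6, 6.8 and 4.5.1 all point to that list.
- In 7.2, state that these events are recorded to 90 days after the last pembrolizumab dose or the start of new anti-cancer therapy, whichever is earlier. This matches footnote 5 and 7.3.1 and gives the window a defined start. Section 7.3.4.1 words its own cut-off differently (30 days after cessation if new therapy starts), so the same edit should say whether that difference is intended.
- Reconcile the 24-hour and 2-working-day clauses in 7.3.4.1.

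The cost is a wording amendment and eCRF guidance. The follow-up visit about 60 days after end of treatment already exists, so no visit or procedure is added. The downside is a few more non-serious entries and a slightly higher reported rate of immune-related events.
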